Visit																																																	
Trial day	-14 to -1	1	8	15	22	29	36	43	50	57	64	71	78	85	92	99	106	113	120	127	134	141	148	155	162	169																							
Visit window, days																																																	
Pharmacokinetics ^{h,n}		X	X	X	X	X ^o	X ^o	X ^o	X ^o	X ^o	X ^o	X ^o	X ^o	X ^o	X ^o	X ^o	X ^o	X ^o	X ^o	X ^o	X ^o	X ^o	X ^o	X ^p	X	X	X	X	X	X																			
Randomization ^f		X																																															
IMP administration ^s		X	X	X	X	----- qw or q2w administration -----																																											
Caregiver informed consent form ^t																										X																							
IMP (self-)administration training ^{s,u}																										X																							
Collecting information related to hospitalization for ITP management		----- X -----																																															
Concomitant therapies/procedures ^v		----- X -----																																															
Adverse events ^v		----- X -----																																															

FACT-Fatigue=Functional Assessment of Chronic Illness Therapy-Fatigue; FACT-Th6=Functional Assessment of Cancer Therapy-Th6; IMP=investigational medicinal product; ITP=immune thrombocytopenia; ITP-PAQ=ITP-Patient Assessment Questionnaire; qw=weekly; q2w=every other week; SF-36 (v2)=Short Form 36 (version 2); WHO=World Health Organization

^a **Trial Period:**

Screening Period: maximum 14 days

Treatment Period: Weekly subcutaneous (SC) IMP administrations for visit 1 up to and including visit 4. As of visits 5 to 16, a qw or q2w IMP administration schedule will be followed. From visits 17 to 24, participants will be fixed on the dose schedule they were receiving at visit 16 or at the last visit at which IMP was administered (ie, either qw or q2w). There is a permissible visit window of +2 days during the treatment phase as well as the follow-up period. Every effort should be made to schedule every visit on the exact day (which is relative to baseline randomization [visit 1]).

The frequency (ie, qw or q2w) of IMP administrations depends on predefined criteria set forward in Section 6.5 of the protocol.

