6.5. Screening and Treatment

After the informed consent has been obtained, the participant will be screened (screening period of maximum 14 days) at the investigative site for eligibility based on the inclusion and exclusion criteria defined in Section 5.1 and Section 5.2, respectively.

The assessments as specified in the SoA, Section 1.3 will be performed during screening.

All participants will initially receive qw SC injections from visit 1 to 4 (consecutive administrations of IMP should be at least 5 days apart).

Based on the platelet counts as of visit 2, the dosing frequency can be altered from visits 5 to 16 (consecutive administrations of IMP should be at least 5 or 12 days apart for the qw or q2w administration schedule, respectively) according to the following rules (the change in dosing frequency will occur at the current visit):

- Reduce from qw to q2w in participants having platelet counts of $\geq 100 \times 10^9/L$ for 3 out of 4 consecutive visits (the fourth visit being the current visit), and having a platelet count of $\geq 100 \times 10^9/L$ at the last of these 4 visits
 - OR –
 - Reduce from qw to q2w in participants having platelet counts of $\geq 100 \times 10^9/L$ for 3 consecutive visits
 - Note: In this case, no IMP will be administered at the last visit confirming the qualifying platelet counts of $\geq 100 \times 10^9/L$.
- Increase from q2w to qw in participants whose platelet counts drop to $< 100 \times 10^9/L$ on 2 consecutive visits
 - OR –
 - $< 30 \times 10^9/L$ at 1 visit
 - OR –

in participants who receive rescue therapy (see Section 6.6.4)

- Postbaseline platelet count can be performed within 1 day of the next procedure as per SoA (both dosing and nondosing visit), allowing the results to be incorporated into the criteria above.

From visits 17 to 24, the dosing frequency is fixed for each individual participant (ie, either qw or q2w regimen), based on the regimen the participant was receiving at visit 16 or at the last visit at which IMP was administered.

Exceptions to the fixed dosing frequency are:

- Continued qw dosing for participants requiring rescue therapy
- Continued q2w dosing for participants resuming IMP when the platelet count falls to $<150 \times 10^9/L$ after having had platelet counts $>400 \times 10^9/L$

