8. TRIAL ASSESSMENTS AND PROCEDURES

- Trial procedures and their timing are summarized in the SoA (Section 1.3).
- Adherence to the trial requirements, including those specified in the SoA (Section 1.3), is essential and required for trial conduct.
- When a protocol-required procedure cannot be performed, the investigator will document the reason, and any corrective and preventive actions that he/she has taken to ensure that the normal processes are adhered to, in source documents. The trial team should be informed of these incidents in a timely manner. This will be considered a protocol deviation and will be recorded accordingly.
- At screening, all eligibility assessments should be performed after obtaining informed consent.
- All screening evaluations must be completed and reviewed to confirm that participants meet all eligibility criteria before randomization.
- The investigator will maintain a screening log to record details of all participants screened and confirm eligibility or record reasons for screening failure, as applicable.
- Each participant should attend each trial visit on the designated days. There is a permissible visit window of +2 days during the treatment period as well as the end-of-treatment visit and follow-up period. Every effort should be made to schedule every visit on the exact day (which is relative to baseline [visit 1]) as described in the SoA (Section 1.3).
- From the signature of informed consent until the last trial-related activity, all AEs that occur and all concomitant medications that are taken and procedures performed, whether allowed or not, during the trial are to be recorded on the appropriate pages on the eCRF.
- During the IMP treatment period, all assessments and procedures must be performed before the start of the IMP administration, except for ECG assessment and the continuous assessment of AEs and the recording of concomitant therapy and procedures.

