Derivation: a participant is considered a responder if he/she shows platelet count of at least $100 \times 10^9/L$ and the absence of bleeding events (WHO=0) for at least 2 separate, consecutive occasions which are at least 7 days apart (in case of missing visits (phantom records), the target date will be used). Platelet count after one of the main intercurrent events will be handled in the same way as for extent of disease control (section 4.1.2.2), but imputing $< 100 \times 10^9/L$ instead of $< 50 \times 10^9/L$. Missing values not due to one of the main intercurrent events will be handled as follows: if platelet count $\geq 100 \times 10^9/L$ for the previous and the next analysis visit, the platelet count will be imputed with $\geq 100 \times 10^9/L$, otherwise with $< 100 \times 10^9/L$. Missing bleeding assessments after one of the main intercurrent events will not be imputed. For 'increase of dose and/or frequency of concurrent ITP therapies or start of a new concurrent ITP therapy' and 'initiation of rescue therapy' the whole treatment period should be taken into account. In case of rescue therapy, the bleeding events will not be imputed for 4 weeks strictly after the initiation of the therapy (the initiation of the therapy is the start date/time of the administration of the first rescue treatment for that occurrence). Missing bleeding assessments for other reasons than the main intercurrent events will be imputed as described in section 4.1.2.5 (approach 3)

13) Proportion of participants with an IWG-Response¹².

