Derivation: a participant is considered a responder if he/she shows platelet count of at least $30 \times 10^9/L$ and at least a 2-fold increase of platelet count from baseline and the absence of bleeding events (WHO=0) for at least 2 separate, consecutive occasions which are at least 7 days apart (in case of missing visits (phantom records), the target date will be used). Platelet count after one of the main intercurrent events will be handled in the same way as for extent of disease control (section 4.1.2.2), but imputing $< 30 \times 10^9/L$ instead of $< 50 \times 10^9/L$. If platelet count $\geq 30 \times 10^9/L$ for the previous and the next analysis visit, the platelet count will be imputed with $\geq 30 \times 10^9/L$, otherwise with $< 30 \times 10^9/L$. In the same way, if the previous and the next analysis visit indicates a 2-fold increase, the missing 2-fold increase will be imputed with "Yes", otherwise "No". Missing bleeding assessments after one of the main intercurrent events will not be imputed. For 'increase of dose and/or frequency of concurrent ITP therapies or start of a new concurrent ITP therapy' and 'initiation of rescue therapy' the whole treatment period should be taken into account. In case of rescue therapy, the bleeding events will not be imputed for 4 weeks strictly after the initiation of the therapy (the initiation of the therapy is the start date/time of the administration of the first rescue treatment for that occurrence). Missing bleeding assessments for other reasons than the main intercurrent events will be imputed as described in section 4.1.2.5 (approach 3).

14) Proportion of participants with an Initial Response¹³.

Derivation: a participant is considered a responder if he/she shows platelet count of at least $30 \times 10^9/L$ and a 2-fold increase of platelet count from baseline at analysis visit

	Statistical Analysis Plan	
ARGX-113-2004	Final analysis	Final 1.0 of 7NOV2023

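### The 7-day spacing rule for IWG response and IWG complete response can reject an unbroken three-visit run that it would accept if the middle visit had been missed

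*SAP*

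**What the plan says.** SAP 4.1.2.3 defines IWG complete response (item 12) and IWG response (item 13) by a platelet criterion plus absence of bleeding on "at least 2 separate, consecutive occasions which are at least 7 days apart (in case of missing visits (phantom records), the target date" is the one used). That parenthesis is the only rule on dates in either item. Neither item says which date applies to a visit that took place, and neither gives a tolerance.

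Both items impute a missing platelet result as qualifying only if the previous and the next analysis visit both qualify. Bleeding follows approach 3 in SAP 4.1.2.5, which imputes no bleeding only if the nearest available assessments on both sides are free of bleeding.

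On scheduling, Protocol section 8 says: "There is a permissible visit window of +2 days during the treatment period as well as the end-of-treatment visit and follow-up period". Protocol 1.3 and section 8 count every visit day from baseline, so a late visit does not move the next target day. Protocol 6.5 sets a dosing interval that allows the same closeness ("consecutive administrations of IMP should be at least 5 days apart") and lets the blood draw differ from the visit day: "Postbaseline platelet count can be performed within 1 day of the next procedure as per SoA".

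**The concern.** The 7-day threshold equals the nominal interval between visits. A visit that runs late, followed by one that runs less late, therefore gives a pair that complies with the protocol but fails the spacing rule. If consecutive means adjacent, a participant can qualify without a break over 12 days and still have no acceptable pair.

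The date rule also treats missed and attended visits differently. A missed middle visit takes its target date, and this can create the 7-day gap that the attended visit lacked. More complete data then give a worse outcome.

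There is a smaller gap as well. Each occasion combines a platelet count and a bleeding score, which may fall on different days, and the SAP does not say which date measures the interval. Two programmers could derive different responders.

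Both endpoints are named secondary endpoints, analysed with the same Cochran-Mantel-Haenszel method as the primary (SAP 4.1.3.2). Their frequency tables are marked for top-line reporting (SAP 8.1).

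**Working it through.** The plan states no figure for this, so there is none to reproduce.

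**Inputs**
- Target days: week 3 = 22, week 4 = 29, week 5 = 36 (SAP Table 4).
- Delay w of each visit: 0, 1 or 2 days (Protocol section 8).
- Date of a missed visit: its target day, so w = 0 (SAP items 12 and 13).
- The documents give no distribution of delays. The shares below are assumptions.

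**Gap between adjacent visits**

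Gap = 7 + w(next) − w(this). With w in {0, 1, 2} the possible gaps are 5, 6, 7, 8 and 9 days. The gap is under 7 exactly when w(next) < w(this).

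**The example**
- Weeks 3, 4 and 5 all qualify, on days 24, 30 and 36 (delays 2, 1, 0).
- All attended: 30 − 24 = 6 and 36 − 30 = 6. No adjacent pair reaches 7 days, so the participant is a nonresponder, although the run spans 36 − 24 = 12 days.
- Week 4 missed: both neighbours qualify, so week 4 is imputed as qualifying and dated day 29. Then 36 − 29 = 7, and the participant is a responder.

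This holds generally inside the window. With the middle visit of a three-visit run missed and imputed, the second gap is 7 + w(third) − 0, which is never below 7.

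**How often a run fails**

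A run fails if every adjacent gap is under 7, so the delays must fall strictly from visit to visit.
- Two visits: P = (1 − p0² − p1² − p2²) / 2.
- Three visits: only delays 2, 1, 0, so P = p2 × p1 × p0.
- Four or more: impossible with three possible delays, so P = 0.

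| Assumed shares at 0/1/2 days late | Two-visit run | Three-visit run | Four or more |
|---|---|---|---|
| 90/7/3% | (1 − 0.81 − 0.0049 − 0.0009)/2 = 9.2% | 0.03 × 0.07 × 0.90 = 0.2% | 0 |
| 80/15/5% | (1 − 0.64 − 0.0225 − 0.0025)/2 = 16.8% | 0.05 × 0.15 × 0.80 = 0.6% | 0 |
| 70/20/10% | (1 − 0.49 − 0.04 − 0.01)/2 = 23.0% | 0.10 × 0.20 × 0.70 = 1.4% | 0 |
| Equal thirds | (1 − 3/9)/2 = 33.3% | 1/27 = 3.7% | 0 |

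If the platelet draw may also fall one day before the visit, gaps run from 4 to 10 days. Three-visit runs then fail in 2.0% of cases (10/70/15/5% at −1/0/+1/+2 days) to 6.25% (equal quarters), four-visit runs in 0.05% to 0.4%, and longer runs never.

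**Effect of the fix**

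The first and last visits of a three-visit run are 14 + w(third) − w(first) days apart. That is at least 12 days, or 11 with an early draw, so every such run passes once its ends may be paired.

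**The case against.** The strongest reply is that the 7-day separation is part of the SAP's definition, which cites an external working-group standard. A participant with two counts 5 days apart does not meet it. A reader might infer that true two-visit responders are being scored as nonresponders. The documents do not support that: it would require an intention to accept any two weekly visits whatever their spacing, and no section says so. This part of the reply stands, and the 9% to 33% for two-visit runs should not be read as an error rate.

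A reader might also infer that a missed visit is accepted wherever an attended late one is rejected, for example week 4 on day 31 followed by week 5 on day 36. The imputation rule prevents it there. Week 4 would be imputed as qualifying only if week 3 also qualified. In-window week 3 falls on days 22 to 24, which is 7 to 9 days before day 31, so the attended run already passes. Inside the +2 window the inversion needs delays of exactly 2, 1 and 0.

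Two further points are fair. The use of actual dates is inferred from the rule for missed visits; the SAP does not state it. And if two consecutive occasions may mean the two ends of an unbroken run, three-visit runs already pass. Both points show that the text leaves the derivation open; they do not settle it.

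Finally, the rule is the same in both arms and the endpoints carry no alpha. The primary endpoint and the three platelet-based key secondary endpoints count analysis visits, the bleeding endpoint has no spacing rule, and initial response is judged at week 5 alone. None of these is affected.

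**Conclusion.** A narrow defect remains. On a literal reading with actual dates, an unbroken three-visit run spanning 12 days can be scored as a nonresponse, while the same run with its middle visit missed and imputed is a response. Inside the +2 window this concerns about 0.2% to 3.7% of three-visit runs and no run of four or more. It changes a participant's status only if no other run in the treatment period qualifies.

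These figures rest on assumed, independent delays, on all visits being in window, and on consecutive meaning adjacent. The protocol asks sites to aim for the exact day, which favours the low end.

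A reader might infer a material bias in the treatment comparison. The documents do not show one: they give neither the distribution of visit delays nor the frequency of short runs in either arm. This is a small clarification to secondary endpoints outside alpha control.

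**What to change.** In SAP 4.1.2.3, items 12 and 13, count a participant as a responder if any two qualifying occasions are at least 7 actual days apart with no nonqualifying occasion between them. State which date measures the interval when the platelet draw and the bleeding assessment fall on different days. This keeps the 7-day condition, removes the inversion, and still excludes two-visit runs of 5 or 6 days.

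If the sponsor wants to know how much those two-visit runs matter, a sensitivity analysis can accept adjacent scheduled visits that lie within the protocol's visit window.

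Spacing should not be moved to target days for all visits without a minimum actual gap. Analysis windows in SAP Table 4 run 3 days either side of target and take in unscheduled counts. A count on day 32 (week 4) and one on day 33 (week 5) would then pass as 7 days apart.

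The cost is a sentence or two in each derivation, a small programming change, and an entry in SAP 6.3, made before unblinding.

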4.1.2.4 OTHER SECONDARY ANALYSES NOT FORESEEN PER PROTOCOL (NOT ALPHA CONTROLLED)

[Redacted text block containing multiple paragraphs of text that has been completely obscured by black bars.]

	Statistical Analysis Plan	
ARGX-113-2004	Final analysis	Final 1.0 of 7NOV2023

[Redacted content]

	Statistical Analysis Plan	
ARGX-113-2004	Final analysis	Final 1.0 of 7NOV2023

[Redacted text block]

[Redacted text block]

[Redacted text block]

[Redacted text block]

Table 10:

[Redacted table content]

[Redacted text block]

[Redacted text block]

[Redacted text block]

[Redacted text block]

[Redacted text block]

Table 11:

[Redacted table content]

	Statistical Analysis Plan	
ARGX-113-2004	Final analysis	Final 1.0 of 7NOV2023

[Redacted text block]

[Redacted text block]

[Redacted text block]

[Redacted text block]

[Redacted text block]

Table 12:

[Redacted table content]

[Redacted text block]

[Redacted text block]

	Statistical Analysis Plan	
ARGX-113-2004	Final analysis	Final 1.0 of 7NOV2023

[REDACTED]

[REDACTED]

[REDACTED]

4.1.2.5 *IMPUTATION*

Missing data (platelet counts) for other reasons than the main intercurrent events will be imputed as follows:

- Approach 1: if platelet count $\geq 50 \times 10^9/L$ for the previous and the next analysis visit, and the previous and next analysis visit are in the treatment phase, the platelet count will be imputed with $\geq 50 \times 10^9/L$, otherwise with $< 50 \times 10^9/L$.
- Approach 2: all missing data will be imputed with $< 50 \times 10^9/L$. This will only be used as sensitivity analysis for the primary endpoint and the first key secondary endpoint.

Intermittent missing data (overall score of WHO bleeding assessment) for other reasons than the main intercurrent events will be imputed as follows:

- Approach 3: If no bleeding event for previous and next analysis visit with available bleeding assessment result (which can enclose several successive missing bleeding assessments), and the previous and next analysis visit are in the treatment phase, impute with no bleeding event, otherwise impute with bleeding event. No imputation will be done after the last available bleeding assessment in the treatment phase.

4.1.3 *Statistical analysis*

Wherever the stratification factors will be used in the efficacy analyses, the actual values of these will be used and not the ones coming from the randomization.

Summary statistics will be provided in terms of actual values and changes from baseline for platelet count in the chronic and the overall FAS population. All analysis visits as expected per SoA (including the follow-up phase) will be shown.

Frequency tabulations will be provided of the percentage of responders with sustained platelet count (primary endpoint) in participants with chronic ITP and overall and by stratification factors (receiving concurrent ITP therapies at baseline [yes/no], history of splenectomy [yes/no]) and baseline platelet count. The table in the overall population will be repeated by subgroup and ADA participant classification. The table for participants with chronic ITP will be repeated for the complementary analysis using the treatment policy strategy.

Frequency tabulations will be provided of the percentage of responders with sustained platelet count (different definitions excluding primary endpoint) and of the percentage

	Statistical Analysis Plan	
ARGX-113-2004	Final analysis	Final 1.0 of 7NOV2023

of responders with overall response (week 1 – 24 and week 1 – 12) in the overall population. Frequency tabulations will also be provided for all different response definitions for platelet count as defined in section 6.1. The response rates and differences in response rate (efgartigimod-placebo) will be shown together with the 95% Agresti-Min¹⁴ confidence limits. The tabulation of the sustained platelet count response (week 19 – 24) in the overall population will be repeated by subgroup.

For the different endpoints on extent of disease control, summary statistics will be provided on the number of cumulative weeks of disease control in the overall population. For the first key secondary endpoint extent of disease control will also be summarized for the chronic population and by stratification factors and baseline platelet count. This first key secondary endpoint summary table for the overall population will also be repeated by subgroup. Furthermore, a table with Kaplan-Meier (KM) estimates will be displayed by randomized treatment arm for the first key secondary endpoint (complementary analysis).

Summary statistics will be provided for the different definitions of number of bleeding events in the overall population. A frequency tabulation will be provided of the number and percentage of bleeding events and repeated for the subgroup on sustained platelet count response (week 19 – 24). The overall severity score at each analysis visit and the worst-case overall severity score will be tabulated.

Summary statistics will be provided in terms of actual values and changes from baseline for PRO scores (FACIT-Fatigue, FACT-Th6) and QoL (SF-36, ITP-PAQ) in the overall population. All analysis visits as expected per SoA (including the follow-up phase) will be shown.

Summary statistics will be provided for the rate of receipt of rescue therapy in the overall population. A frequency tabulation will be provided of the number of rescue therapies (occurrences) received.

Frequency tabulations will be provided of the proportion of participants for whom dose and/or frequency of concurrent ITP therapy have increased at week 12 or later.

KM estimates will be provided for time to platelet count response ($\geq 50 \times 10^9/L$ and $\geq 100 \times 10^9/L$) and time to platelet count $\geq 50 \times 10^9/L$ or $\geq 100 \times 10^9/L$ in the overall population. KM curves and median time to platelet count response will be displayed by randomized treatment.

Summary statistics will be provided in terms of actual values and changes from baseline for IPF# and IPF% in the overall population. All analysis visits as expected per SoA (including the follow-up phase) will be shown.

Statistical inference will be conducted as described below. All statistical comparisons will be made using two-sided tests at the 0.05 significance level unless specifically stated otherwise. Sensitivity analyses will be done for the primary and key secondary endpoints by using the PP population (PP-chronic). The primary and first key secondary endpoint will also be repeated by use of approach 2 for imputing missing values as sensitivity analysis. A complementary analysis using the treatment policy strategy will be done on the primary and the first key secondary endpoint. Furthermore, a complementary analysis will be done on the first key secondary endpoint extent of disease control using a Cox proportional hazards regression model.

	Statistical Analysis Plan	
ARGX-113-2004	Final analysis	Final 1.0 of 7NOV2023

Main intercurrent events occurrence according to the above definitions in section 4.1.2.1 and 4.1.2.2 will be tabulated and listed.

4.1.3.1 *FIXED-SEQUENCE TESTING PROCEDURE*

To control the type I error for the primary and secondary endpoints (alpha controlled), the primary efficacy endpoint will be tested at the 5% 2-sided alpha level and will act as gatekeeper for the testing of secondary endpoints. The primary endpoint and secondary endpoints will be tested in a strict hierarchical order as listed below to control the type I error (for definitions see section 4.1.2.1 and 4.1.2.2). If a certain endpoint turns out to be non-significant at the 5% significance level, based on the p-value, subsequent endpoints will no longer be evaluated.

- Primary endpoint: the proportion of participants with chronic ITP with a sustained platelet count response defined as achieving platelet counts of at least $50 \times 10^9/L$ for at least 4 of the 6 visits between week 19 and 24 of the study.
- The extent of disease control defined as the number of cumulative weeks over the planned 24-week treatment period with platelet counts of $\geq 50 \times 10^9/L$ in the participant population with chronic ITP.
- The proportion of participants in the overall population (chronic and persistent ITP) with a sustained platelet count response defined as achieving platelet counts of at least $50 \times 10^9/L$ for at least 4 of the 6 visits between week 19 and 24 of the study.
- Proportion of participants in the overall population achieving platelet counts of at least $50 \times 10^9/L$ for at least 6 of the 8 visits between week 17 and 24 of the study.
- The incidence and severity of the WHO-classified bleeding events in the overall population.

4.1.3.2 *COCHRAN-MANTEL-HAENSZEL*

The primary endpoint, sustained platelet count, will be analyzed using a Cochran-Mantel-Haenszel statistic stratified for each stratum formed by the combination of the stratification factors. The stratification factors will be history of splenectomy (yes versus no) and receiving concurrent ITP therapies at baseline (yes versus no) and baseline platelet count level category ($< 15 \times 10^9/L$ versus $\geq 15 \times 10^9/L$). The treatment effect will be presented as the odds ratio together with its exact 95% confidence interval (CI)¹⁵ and 2-sided p-value. The MH estimator¹⁶ will be used for the odds ratio (OR), except in case of empty cells for all strata within one treatment, in which case the logit estimator¹⁷ will be used. An OR of more than 1 represents a higher response rate for efgartigimod compared to placebo. In addition, an adjusted difference of the proportions with its 95% confidence (Klingenberg approach) will be provided.

Missing data due to a reason of one of the main intercurrent events as described above (see section 4.1.2.1) will be analyzed as a non-responder (composite variable strategy). Missing data for other reasons will be imputed as described in section 4.1.2.5, approach 1. The analysis will be repeated with approach 2 as sensitivity analysis for the primary endpoint.

	Statistical Analysis Plan	
ARGX-113-2004	Final analysis	Final 1.0 of 7NOV2023

All secondary endpoints related to sustained platelet count response, overall platelet count response, and IWG derived endpoints (ie, complete IWG response, IWG response and initial response) will be analyzed in the same manner as this primary endpoint.

For the primary endpoint only, the analysis will be repeated where the main intercurrent events will be handled by using the ‘treatment policy’ strategy (see section 4.1.2.1).

